Although the effect of pre-procedural physical conditioning on TAVR patients has not been studied, there is significant evidence that pre-procedural physical conditioning, or “prehabilitation,” is beneficial to patients undergoing cardiac surgery. Pre-procedural conditioning has been shown to decrease both ICU and hospital length of stay in patients undergoing coronary artery bypass grafting surgery (CABG) as well as improve physical functioning after surgery.(10)(11) Additionally, a recent meta-analysis concluded that pre-procedural conditioning is effective at reducing postoperative complication rates and length of hospital stay after cardiac surgery.(12)

Patients with severe symptomatic aortic stenosis are at high risk for adverse cardiac event or death and they are advised to only perform activities requiring mild exertion. However, monitored exercise testing in these patients has been shown to be safe.(13,14) In addition, current guidelines recommend monitored exercise testing in patients with severe aortic stenosis and absent or equivocal symptoms.(15) As such, the modest exertion required for physical therapy in a monitored environment is predicted to carry a very low risk.

Decreased exercise capacity and high frailty scores have been shown to be a strong determinant of mortality and adverse events in patients with aortic stenosis. However, implementation of a systematic and monitored physical therapy program to improve exercise capacity and modify frailty scores prior to a major intervention such as TAVR has never been performed. Nor have the outcomes of such a monitored program been evaluated.

Objectives

In this pilot study, we aim to identify patients undergoing TAVR who are at elevated risk for adverse clinical events due to decreased exertional capacity and physical deconditioning. We aim to determine if monitored pre-procedural physical therapy is safe in these patients. Lastly, we aim to assess the efficacy of prehabilitation a) to improve physical functioning by the time of TAVR and to sustain benefit through 30 days post-procedure; and b) to determine its effect on post-procedural length-of-stay, clinical outcomes, and quality of life.

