As a precursor to a large, definitive randomized clinical trial, this pilot study will examine the components of patient recruitment and retention, assessment of exertional capacity, and program implementation of this intervention with the goal that they will be employed in a larger scale study and possibly to all TAVR programs in the United States. To this end, all components of this study were chosen not only for clinical efficacy, but also for cost effectiveness and ease of implementation into current “real world” TAVR programs.

Primary Efficacy Outcomes

- **Functional exercise capacity – Change in 6 Minute Walk Test (6MWT)**
Measure: Does prehabilitation improve the subject’s functional exercise capacity from first PT assessment to pre-procedure assessment and first PT assessment to one month post-procedure, as measured by the 6MWT?

Secondary Efficacy Outcomes

- **Mobility – Timed Up-and-Go (TUG) test**
Measure: Does prehabilitation improve the subject’s mobility from first PT assessment to pre-procedure assessment and first PT assessment to one month post-procedure, as measured by the TUG test?
- **Balance – Four Square Step Test (FSST)**
Measure: Does prehabilitation improve the subject’s balance from first PT assessment to pre-procedure assessment and first PT assessment to one month post-procedure, as measured by the FSST?
- **Discharge disposition**
Measure: Does prehabilitation make it less likely that a patient will require a higher level of care at discharge than they required prior to admission (for example, arrive from home and discharged to home)?
- **Length of stay in Intensive Care Unit (hours)**
- **Total hospital length of stay (days)**

- **Change in quality of life**
Measure: Does Kansas City Cardiomyopathy Questionnaire score change from first PT assessment to one month post-procedure?
- **30-day readmission**
Measure: Does the subject have a 30-day readmission post-procedure?

Safety Outcomes

- Syncope
- Major adverse cardiac events (MACE)
- Falls and musculoskeletal adverse events
- Adverse events from other complications
- Serious adverse events, including those that require hospitalization

Hypotheses

1. Monitored pre-procedural physical therapy is safe for patients identified as frail who are undergoing transcatheter aortic valve replacement.
2. Monitored pre-procedural physical therapy in patients to undergo transcatheter aortic valve replacement will result in:

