 - a. An objective improvement in patient physical function from baseline to the time of procedure and 30 days post-procedure.
 - b. Decreased length of stay and improved clinical outcomes and quality of life.

Study design

This is a pilot study involving a cohort of seventy subjects randomized to either participate (treatment group) or not participate (control) in a prehabilitation program prior to undergoing a TAVR. After providing informed consent, subjects will be randomized via REDCap™ to a treatment or control group. Thirty five subjects will be randomized to each group. Subject number and randomization will be assigned by REDCap™. All subjects in this pilot study will be followed from the intake assessment through one year post-procedure.

Study population and recruitment methods

The research coordinator will identify potential TAVR patients using clinic schedules and then conduct a chart review to verify that they meet inclusion/exclusion criteria. Patients will be approached by the research coordinator regarding the study. The research coordinator will verbally explain the study and provide time for questions and discussion. The patient will be provided with a written copy of the consent document to read and review. The research coordinator will set up an additional appointment to assess understanding and verify willingness to participate. The patient will then sign the consent if interested in participation.

Inclusion and exclusion criteria:

Inclusion Criteria

- Subject must be ambulatory (with or without an assist device)
- Subject has severe aortic stenosis and is felt an appropriate candidate for TAVR by the Heart Team.

- Subject requires 6.0 seconds or longer to complete a 15ft walk test
- Subject must be able to move between sitting and standing without assistance from another person.
- Subject has adequate iliac and femoral arterial anatomy to allow for TAVR via transfemoral access
- Subject is 18 years of age or greater
- Subject is willing to give consent and participate in the study

Exclusion Criteria

- Subject is incapable of following instructions
- Subject is unable to meet the minimum required physical therapy visits
- Subject has other medical conditions rendering it unsafe, in the opinion of the Principal Investigator and physical therapy staff, to perform a 6 Minute Walk Test or physical therapy conditioning prior to TAVR
- Subject has significant severe un-revascularized epicardial coronary disease.

Role of subjects

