Comorbidities (all diagnoses codes)	X					X	X
Study comorbidities 
 • Current medications • Pre-existing conditions related to reduced exercise capacity, mobility, and/or balance; including physical disabilities unrelated to aortic stenosis 	X					X	X

6MWT	X		X			X	X
TUG Test	X		X			X	X
FSST	X		X			X	X
Kansas City Cardiomyopathy Questionnaire	X		X			X	X
Date and time of visit		X	X			X	X
Adverse events		X	X*			X	X
• MACE							
• Syncope							
• Falls and musculoskeletal adverse events							
• Adverse events from other complications							
• Serious adverse events, including those that require hospitalization							
Type and size of valve used for TAVR				X			
Adverse events during surgery				X			
Discharge disposition					X		
Length of stay					X		
• In ICU (hours)							
• Total hospital (days)							
Cost of stay (assessed by total charges accrued during hospitalization)					X		
Inpatient readmission information						X	X

*This should be assessed in both groups prior to TAVR to see if the control arm experienced similar adverse events independent of prehab therapy.

Data analysis and Data Monitoring

Evaluate primary, secondary and the safety outcomes (as listed in the protocol) by conducting a data integrity check to assure reliability of the data. Once all data inconsistencies are corrected data analysis should occur. The analysis would compare 2 groups: the study group and the control. Based on the objectives, the data will be analyzed using the required statistical tests; categorical variables would be compared using the Fishers Exact test or Chi-square tests and measurement data would be compared using the independent sample t-test or Mann Whitney U test. All analysis will be evaluated using parametric tests unless the data is not normal in which case non-parametric tests will be used.

As needed interim analysis of primary, secondary and safety outcomes by study group (treatment vs. no treatment) will be conducted. If a decision is made to stop the study early, this limitation should be expressed in any project write-up. If at the conclusion of the assessment of the primary outcome (6 minute walk test) there is a significant difference between the study groups ($p < .05$) a Power analysis will be conducted, and if the Power is greater than 80%, a recommendation to conclude the study could be made – if this is done there is risk of making a type II error and should be shared in any project write up.

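### The plan sets out to show that prehabilitation is safe, but the only between-arm method it gives for categorical safety events is a test of difference, which at 35 per arm cannot support that conclusion.

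*Combined protocol and SAP*

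**What the plan says.** The Objectives section says "We aim to determine if monitored pre-procedural physical therapy is safe in these patients". The first item under Hypotheses turns this into a positive statement: "Monitored pre-procedural physical therapy is safe for patients identified as frail who are undergoing transcatheter aortic valve replacement". The list under Safety Outcomes covers syncope, MACE, falls and musculoskeletal events, other adverse events and serious adverse events. It attaches no acceptable rate or decision rule to any of them.

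Under Study design, "Thirty five subjects will be randomized to each group". No sample-size calculation is given.

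The section Data analysis and Data Monitoring treats primary, secondary and safety outcomes together. It says "The analysis would compare 2 groups: the study group and the control", and that "categorical variables would be compared using the Fishers Exact test or Chi-square tests". No test is assigned to the safety outcomes by name. Fisher or chi-square applies to them because they are categorical and are covered by that section. Interim comparisons by group, safety included, may be made as needed. A DSMB is to review all adverse and serious adverse events. A footnote to the visit chart asks for adverse events to be assessed in both arms before TAVR.

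**The concern.** A test of difference takes no difference as its null hypothesis. Rejecting the null is evidence of a difference; failing to reject it leaves open every excess that the data cannot exclude. A claim of safety needs a statement of how large a rate, or an excess, remains plausible. That takes an interval, or a margin fixed beforehand, and the plan has neither.

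If the analysis section is followed as written, the formal result bearing on Hypothesis 1 is a p-value for each event type. In a study this small, a moderate excess could be reported as no significant difference and then be taken as support for the hypothesis. The Objectives describe the pilot as leading to a definitive trial and possibly to wider use in TAVR programmes. The Study Rationale describes the patients as at high risk of cardiac events or death. The safety conclusion is therefore likely to be carried forward.

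**Working it through.** **Inputs.** From the documents: 35 subjects per arm, two arms, Fisher's exact or chi-square for categorical outcomes. The 0.05 level is stated only for the 6-minute walk; two-sided 0.05 is assumed here for safety. The documents give no event rates, so those below are assumptions. All 35 per arm are taken as evaluable; fewer would make matters worse. The plan has no safety calculation to reproduce.

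**1. What zero events would show.** The exact (Clopper-Pearson) two-sided 95% upper limit for 0 of n is 1 − 0.025^(1/n). With n = 35 this is 1 − 0.025^(1/35) = 0.100, or 10.0%. One event in 35 gives an upper limit of 14.9%, and two give 19.2%.

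**2. What excess the test would flag.** Take 5/35 treated against 0/35 control, an observed excess of 14.3 points.
- Fisher, two-sided: 2 × C(35,5)/C(70,5) = 2 × 324,632/12,103,014 = 0.054.
- Uncorrected chi-square: N(ad − bc)² divided by the product of the margins = 70 × (5×35 − 30×0)² / (35×35×5×65) = 5.385 on 1 df, p = 0.020.
- Yates-corrected chi-square: 70 × (175 − 35)² / 398,125 = 3.446, p = 0.063.

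For 7/35 against 1/35, Fisher gives 0.055 and uncorrected chi-square 0.024. By Fisher, significance needs 6 treated events when there are no control events (p = 0.025), or 8 when there is one (p = 0.028).

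**3. Power.** This is the sum, over all pairs (x, y) with p < 0.05, of Bin(x; 35, p₁) × Bin(y; 35, p₂).

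| Treated vs control (assumed) | Fisher | Uncorrected chi-square |
|---|---|---|
| 10% vs 5% | 3% | 13% |
| 15% vs 5% | 14% | 31% |
| 20% vs 5% | 33% | 52% |
| 20% vs 10% | 13% | 22% |
| 30% vs 5% | 74% | 84% |

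Across assumed control rates of 1% to 20%, Fisher reaches 80% power only for excesses of about 23 to 34 points (for example 24% vs 1%, or 54% vs 20%).

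**4. What an interval would show.** For 5/35 against 0/35 the Newcombe 95% interval for the risk difference is 1.5 to 29.4 points. For 0/35 against 0/35 it is −9.9 to +9.9 points. Both results are informative, and neither would be called proof of safety.

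**5. Would a margin-based test fit?** With equal true rates p, one-sided 0.025 and 80% power, n per arm = (1.960 + 0.842)² × 2p(1 − p)/margin². For an assumed 10-point margin and p = 5% this is 7.849 × 0.095/0.01 = 74.6, so 75 per arm; for p = 10% it is 142. Estimation therefore suits 35 per arm better than a non-inferiority claim.

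**The case against.** **It is a pilot.** A pilot is not expected to have power for safety events, and Hypothesis 1 may be only a working statement. The first part stands: 35 per arm is not in itself an error. But the Objectives also say that safety is to be determined, so the mismatch between claim and method remains.

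**Other safety review is planned.** A reader might infer that the difference test is the plan's whole provision for safety. The documents do not support that: there is DSMB review, interim comparison as needed, recording of events during conditioning, and assessment of both arms before TAVR. What holds is narrower. None of these gives a criterion or an interval by which safety could be concluded.

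**The test is not blind to harm.** A reader might also infer that the comparison would almost always be non-significant even with clearly more events in the treated arm. That goes too far. Six events against none is significant by Fisher, and Fisher power is 74% for 30% versus 5%. Uncorrected chi-square has roughly even odds at 20% versus 5%. The weakness concerns moderate excesses.

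**The chosen test matters.** Expected event counts in the 5 versus 0 table are 2.5 per arm, where Fisher is the usual choice, so the chi-square result may never be used. The plan does not say which test applies when. Part of the contrast between Fisher's p-value and the Newcombe interval also reflects method, since Fisher is conservative and Newcombe approximate. An interval adds a range of plausible excesses, not a more favourable significance test.

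**Rates would be seen anyway.** Comparing categories normally involves tabulating counts, so crude rates would probably appear. The plan's silence does not exclude them, but it does not commit to intervals either.

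**Conclusion.** The point holds as a mismatch between a positive claim of safety and an analysis that cannot support it. The logic does not depend on the assumed rates; the size of the problem does. With 35 evaluable subjects per arm, an excess of 10 points over an assumed 5% control rate would be missed in 86% of trials by Fisher (100 − 14) and 69% by uncorrected chi-square (100 − 31). For an excess of 15 points the figures are 67% and 48%. A treated arm free of events would still leave a true rate of up to 10.0% plausible.

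It would be wrong to conclude that the sponsor intends to declare safety from a non-significant p-value. The documents do not say so. They leave that reading open and provide nothing better in its place. This is a worthwhile, low-cost improvement to wording and reporting, not a reason to enlarge the pilot.

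**What to change.** In Data analysis and Data Monitoring, add that for each listed safety outcome the number and proportion of subjects with an event will be reported by arm with an exact (Clopper-Pearson) 95% confidence interval, and the risk difference with a 95% confidence interval. Name the interval method for the difference in advance, for example Newcombe. If a test is kept, say which one.

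Reword Hypothesis 1, and the matching sentence in the Objectives, as estimation: to estimate the rates of syncope, MACE, falls and serious adverse events, and the other listed safety outcomes, in each arm and the differences between arms. State that a non-significant test will not be read as showing safety, and that the upper confidence limit will be quoted in any safety conclusion.

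The cost is a protocol wording change and a few table columns, with no added subjects, visits or data. The safety statement will look less favourable than a bare report of no significant difference.

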Title: PreHabilitation for patients undergoing Transcatheter Aortic Valve
Replacement (TAVR PreHab)

NCT# NCT03107897 Unique Protocol ID: TAVR Prehab

Version: January 26, 2022

Principal Investigator: [name], MSc

Title: PreHabilitation for patients undergoing Transcatheter Aortic Valve Replacement (TAVR PreHab)

Version: January 26, 2022

Principal Investigator: [name], MSc

Background

Degenerative aortic stenosis is the most common form of valvular heart disease in developed countries and its prevalence increases with age. Patients with severe aortic stenosis who develop symptoms and are only treated with medical therapy have a very poor prognosis with survival rates as low as 50% at 2 year and 15% at 5 years.(1) Traditionally patients with severe, symptomatic aortic stenosis are treated with surgical aortic valve replacement (SAVR) which significantly decreases mortality and improves quality of life.(2) Unfortunately, many patients suffering with this are deemed too high risk to undergo SAVR and surgical correction is not offered.(3)

Transcatheter aortic valve replacement (TAVR) has emerged as an alternative therapy to surgery for patients with severe, symptomatic aortic stenosis. In TAVR, a bioprosthetic valve is mounted on a catheter, advanced to the aortic annulus, then expanded and deployed inside the native diseased valve. Multiple randomized-controlled trials have shown TAVR to be superior to medical therapy and equal or superior to SAVR in patients with severe symptomatic aortic stenosis and high to prohibitive predicted surgical risk. (4-7) When compared to SAVR, TAVR also offers shorter hospital length of stay and better quality of life at 30 days.

Patients undergoing TAVR are older and have more comorbidities than patients undergoing surgical aortic valve replacement (SAVR) and thus often have high frailty scores. It has recently been shown that the presence of a high frailty score predicts increased 1-year mortality in patients undergoing TAVR.(8) In addition, it has been shown that patients who undergo TAVR “benefit from rehabilitation despite their older age and comorbidities” and that this helps to maintain their independence.(9)

Study Rationale

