Subject Schedule

Subjects in the control arm will undergo all items except the prehabilitation intervention. Subjects in the treatment arm will undergo all items.

Intake Assessment

At this visit, subjects will meet with a member of the Physical Therapy staff who will perform an assessment of the subject's functional exercise capacity, mobility, and balance through the following:

- a. 6MWT
- b. TUG Test
- c. FSST
- d. Kansas City Cardiomyopathy Questionnaire

Other information collected by the research coordinator will be demographic information, subject contact information and comorbidities. Subjects will be randomized at the conclusion of the Intake Assessment.

Prehabilitation (treatment group only)

Based on the results of the Intake Assessment, the physical therapist will determine a course of conditioning specific to each subject; however, each subject will receive a minimum of eight visits and a maximum of 12 over the 3 to 5 weeks prior to the surgery date. Date and time of each visit will be collected. Providers will note the following adverse events that occur during conditioning:

- a. MACE
- b. Syncope, Falls and musculoskeletal adverse events
- c. Adverse events from other complications
- d. Serious adverse events, including those that require hospitalization

Pre-operative Assessment

The final encounter with the subject pre-operatively will perform the same assessments as performed during the Intake Assessment:

- e. 6MWT
- f. TUG Test
- g. FSST
- h. Kansas City Cardiomyopathy Questionnaire

TAVR procedure

Providers will implant the aortic valve and record the following:

- i. Type and size of valve used
- j. Adverse events during surgery

Discharge assessment

Upon discharge, the subject will be assessed for the following:

- k. Discharge disposition
- l. Length of stay in ICU (hours) and total hospital (days)
- m. Cost of stay (assessed by total charges accrued during hospitalization)

30-day Follow-up Assessment

All subjects' electronic health records (EHR) will be monitored for thirty days from the discharge date for the following:

- n. Comorbidities and study comorbidities
- o. Inpatient re-admission information
- p. Cost of stay (assessed by total charges accrued during a readmission hospitalization)
- q. Date and time of visit
- r. Syncope
- s. MACE
- t. Falls and musculoskeletal adverse events
- u. Adverse events from other complications
- v. Serious adverse events, including those that require hospitalization
- w. Mortality

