In addition, patients who undergo pre-procedural physical therapy will do so under the close supervision of the physical therapist and the Research Registered Nurse. The physical therapist and RN will continually assess the patient, ask how the patient is feeling, and ask if they are experiencing any negative symptoms in accordance with the American College of Sports Medicine (ACSM) guidelines (Table 1). Any participant who experiences any significant negative symptoms or exhibits any significant adverse signs will have his/her current active stopped and will be clinically assessed and observed. If the adverse symptoms have not resolved within 20 minutes, the patient, will undergo immediate clinical evaluation and treatment.

Table 1: Indication to stop therapy and assess and observe patient per ACSM guidelines.

 • Onset of angina or angina-like symptoms

 • Drop in SBP of ≥ 10 mmHg with an increase in work rate or if SBP decreases below the value obtained in the same position prior to testing

 • Excessive rise in BP: systolic pressure > 250 mmHg and/or diastolic pressure > 115 mmHg

 • Shortness of breath, wheezing, leg cramps, or claudication

 • Signs of poor perfusion: light-headedness, confusion, ataxia, pallor, cyanosis, nausea, or cold and clammy skin

 • Failure of HR to increase with increased exercise intensity

 • Noticeable change in heart rhythm by palpation or auscultation

 • Subject requests to stop

- | |
|---|
| 
• Physical or verbal manifestations of severe fatigue |
| 
• Failure of the testing equipment |

Benefits

There are no guaranteed benefits from participation in this study. Information gained from the conduct of this study may be of benefit to future patients with the same medical condition.

Compensation / incentives and research-related costs

Those randomized to the physical therapy arm of the study will receive free physical therapy prior to their TAVR procedure.

Participants will receive \$20 for each completed on-site visit to help cover expenses for attending study visits. These expenses include:

- Local travel/parking expenses to and from office visits and tests.

Alternative procedures

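### Before TAVR, scheduled adverse-event recording covers 9 to 13 contacts in the treated arm and one in controls, and the planned between-arm safety comparison is not limited to the check both arms share

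*Combined protocol and SAP*

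**What the plan says.** Treated subjects attend supervised therapy: "each subject will receive a minimum of eight visits and a maximum of 12 over the 3 to 5 weeks prior to the surgery date" (Subject Schedule, Prehabilitation). At those sessions, "Providers will note the following adverse events that occur during conditioning", followed by a list covering MACE, syncope, falls and musculoskeletal events, other complications and serious events. Risks and risk management adds active questioning: "The physical therapist and RN will continually assess the patient, ask how the patient is feeling". Controls follow the same schedule without this phase.

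The visit chart under Research procedures also marks adverse events at the Pre-operative Assessment, with a footnote: "This should be assessed in both groups prior to TAVR to see if the control arm experienced similar adverse events independent of prehab therapy". The Subject Schedule text for that visit does not mention adverse events. It reads "The final encounter with the subject pre-operatively will perform the same assessments as performed during the Intake Assessment" and lists the three physical tests and the quality-of-life questionnaire.

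The electronic health record "will be monitored for thirty days from the discharge date for the following", and the one-year review also counts from discharge. Mortality is listed only in those two reviews, and the chart has no mortality row. The Adverse Events section gives both arms an unscheduled route: events may be volunteered, elicited or observed, and patients are told to contact the study team about significant events between visits.

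Data analysis and Data Monitoring plans to evaluate the safety outcomes, compares the two groups (categorical data by Fisher's exact or chi-square test), and allows interim analyses of safety by group as needed. It does not say which pre-TAVR event records enter the comparison.

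**The concern.** The footnote gives the control arm a specific job: to show which events occur before TAVR without prehabilitation. That works only if events are looked for in much the same way in both arms. Here one arm is questioned repeatedly by a therapist and a nurse over several weeks, and the other is asked once, at the end. A brief dizzy spell or a minor fall is more likely to be recorded in the first setting than recalled in the second.

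If session records and the single control record are combined, a programme with no true effect on risk can appear to cause events. Thin control data also weaken the background rate against which a real excess would be judged. Safety is Hypothesis 1, and the pilot is meant to inform a larger trial, so a distorted comparison would carry forward.

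**Working it through.** **1. Scheduled adverse-event contacts between intake and TAVR**

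| Source | Treated | Control |
|---|---|---|
| Prehabilitation sessions (Subject Schedule) | 8 to 12 | 0 |
| Pre-operative check (visit chart, footnote) | 1 | 1 |
| Health-record review (starts at discharge) | 0 | 0 |
| Total scheduled | 9 to 13 | 1 |
| Unscheduled reporting (Adverse Events section) | yes | yes |

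The intake visit has no adverse-event entry in the chart.

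**2. Subjects who do not reach the pre-operative visit.** Neither arm has a scheduled event or mortality item for them. A treated subject still has records from the sessions attended; a control has unscheduled reporting only. The documents give no rate for missing this visit. If it were 5% to 15% (assumed), then 35 × 0.05 = 1.75 to 35 × 0.15 = 5.25, or about 2 to 5 controls, would have no scheduled pre-TAVR contact.

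**3. What unequal capture could do.** The only planning figure is the sample size: "Thirty five subjects will be randomized to each group", and 35 + 35 = 70 agrees with the stated total. No event rate, safety margin or detection rate is given, so everything below is assumed: the same true risk p in both arms, complete capture in the treated arm, and capture c in controls.

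- Expected recorded counts: 35 × p treated, 35 × p × c control.
- Recorded risk ratio: p / (p × c) = 1/c. For c = 0.9, 0.7 and 0.5 this is 1.11, 1.43 and 2.00, whatever p is.

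The last column is the chance that Fisher's exact test falsely shows an excess in the treated arm. It comes from exact binomial enumeration with 35 per arm. A two-sided 0.05 level is assumed, because the plan states p < .05 only for the walk test.

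| p | c | Expected treated vs control | False treated excess |
|---|---|---|---|
| 20% | 1.0 | 7.0 vs 7.0 | 1.3% |
| 20% | 0.9 | 7.0 vs 6.3 | 2.1% |
| 20% | 0.7 | 7.0 vs 4.9 | 5.4% |
| 20% | 0.5 | 7.0 vs 3.5 | 12.9% |
| 40% | 1.0 | 14.0 vs 14.0 | 1.4% |
| 40% | 0.9 | 14.0 vs 12.6 | 3.3% |
| 40% | 0.7 | 14.0 vs 9.8 | 13.0% |
| 40% | 0.5 | 14.0 vs 7.0 | 35.7% |

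At p = 10% the false-excess chance stays between 0.7% (c = 1.0) and 3.0% (c = 0.5). With equal capture the ratio is 1.00 throughout. The ratio only restates the assumed capture, so the table shows sensitivity and does not estimate the bias.

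**The case against.** Unequal contact is inherent when a supervised programme is compared with none, and this is a 70-subject pilot built for easy implementation. Events in supervised sessions are direct evidence on whether the therapy is safe, and Hypothesis 1 sets no comparative margin. The chart already places the same pre-operative check in both arms, so a like-for-like source exists, and a data safety monitoring board sees all adverse events.

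Most of this stands. It means the between-arm comparison is supporting evidence for Hypothesis 1 and not its whole basis. It does not remove the problem, because the plan compares safety outcomes between groups without confining that comparison to the shared check.

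Three stronger readings are tempting and are not supported:

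- *Control events are counted only if the subject attends the pre-operative visit.* The Adverse Events section allows volunteered, elicited and observed events in both arms and names death as a serious criterion. What is missing is a scheduled method. The unscheduled route relies largely on the patient and on the event seeming significant. That section also defines an adverse event as related to the study, which could screen out the background events the footnote seeks.
- *Unrecorded control deaths show the asymmetry.* The Background cites "survival rates as low as 50% at 2 year and 15% at 5 years" under medical therapy alone. At a constant hazard of ln 2 / 24 = 0.0289 per month, 3 to 5 weeks (0.69 to 1.15 months) gives 2.0% to 3.3%, or about 0.7 to 1.1 deaths among 35. But session recording has no separate mortality item and covers events during conditioning, so a death at home between sessions has no scheduled record in the treated arm either. The figure is also near an upper bound: the source wording is a worst case, and the trial excludes patients whom the cardiologist judges at high risk of an adverse event.
- *All event types are distorted alike.* Hospitalised serious events and MACE plausibly depend less on contact frequency than minor falls or dizziness.

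**Conclusion.** The point holds as a difference in scheduled ascertainment: 9 to 13 contacts against one before TAVR, with unscheduled reporting in both arms and no record review until after discharge. The missing collection for subjects who do not reach the pre-operative visit affects both arms, but more is lost in controls. The likely direction is an inflated treated-arm rate, mainly for milder events. Its size cannot be derived from the documents; the ratios of 1.11 to 2.00 follow entirely from assumed capture of 90% to 50% in controls with complete capture in the treated arm. It would be too strong to say that safety cannot be assessed at all: in-session events remain informative, and the shared pre-operative check is a sound base if the analysis is tied to it. The change should be made, because the plan as written permits pooling session-detected events and comparing them with a single-visit control record.

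**What to change.** 1. Start the event and mortality review of the health record, already planned for 30 days and one year, at randomisation in both arms, and run it to TAVR, death or withdrawal.
2. Add the chart's adverse-event check to the Subject Schedule text for the Pre-operative Assessment. Ask the same structured questions in both arms about the whole period since randomisation, by phone if the visit is missed.
3. State in Data analysis and Data Monitoring that the between-arm pre-TAVR safety comparison uses these common sources only.
4. Report events noted in sessions separately, as a description of the treated arm.

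An in-session event still enters the comparison if the common questions or the record pick it up, so harm from exercise is not excluded by design.

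The cost is protocol wording, an earlier start for an existing review, a short set of questions at an existing visit and some phone calls: a little more coordinator time, with no new staff or procedures. The recorded control event rate will probably rise.
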